### 3.5.2 Prior and Concomitant Medications and Therapies

All therapies (drug or non-drug), including herbal preparations, whether prescribed or over-the-counter, that are used during the study will be recorded in the eCRF. Details include generic and/or brand names of medications, WHO drug dictionary encoding, reason for use, route, dose, dosing frequency, and start and stop dates.

Prior therapies are defined as those with at least one dose/treatment taken before the date of the first dose of study medication.

Concomitant therapies are defined as those with at least one dose/treatment taken between the date of first dose (inclusive) and the date of last dose (inclusive) of durvalumab.

Missing start and stop dates for medications will be imputed using the rules described in Section 4.1.3.

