6.4 Concomitant therapy

The Investigator must be informed as soon as possible about any medication taken from the time of screening until the end of the clinical treatment phase of the study (ie, until 90 days after last dose of IP), including the follow-up period following the last dose of IP.

Any medication or vaccine including over-the-counter or prescription medicines, vitamins, and/or herbal supplements that the patient is receiving at the time of enrolment or receives during the study must be recorded along with:

- Reason for use
- Dates of administration including start and end dates
- Dosage information including dose, unit and frequency

Patients must be instructed not to take any medications, including over-the-counter products, without first consulting with the Investigator.

Restricted, prohibited, and permitted concomitant medications are described in [Table 6](#) and [Table 7](#). Refer also to the Dosing Modification and Toxicity Management Guidelines in Section [8.4.5.1](#).

Table 6 Prohibited concomitant medications

| Prohibited medication/class of drug | Usage |
|---|---|
| Any investigational anticancer therapy other than those under investigation in this study | Should not be given concomitantly while the patient is on study drug |
| mAbs against CTLA-4, PD-1, or PD-L1 other than those under investigation in this study | Should not be given concomitantly while the patient is on study drug |
| Any concurrent chemotherapy, radiotherapy, immunotherapy, or biologic or hormonal therapy for cancer treatment other than those under investigation in this study | Should not be given concomitantly while the patient is on study drug. (Concurrent use of hormones for non-cancer-related conditions [eg, insulin for diabetes and hormone replacement therapy] is acceptable. Local treatment of isolated lesions, excluding TLs, for palliative intent is acceptable [eg, by local surgery or radiotherapy].) |
| Live attenuated vaccines | Should not be given through 30 days after the last dose of IP |

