- Exclusion Criterion 13: Patients who have received cCRT for locally-advanced NSCLC, or who received sCRT with at least 2 concomitant CRT cycles. Prior surgical resection (ie, Stage I or II) is permitted.  
  
Note: Patients whose platinum-based chemotherapy contained gemcitabine and who received sCRT with at least 1 concomitant CRT cycle are excluded from this study.
- Exclusion Criterion 16: Prior exposure to immune-mediated therapy, including but not limited to, other anti-CTLA-4, anti-PD-1, anti-PD-L1, and anti-PD-L2 antibodies, excluding therapeutic anticancer vaccines.
- Deviation 2: The patient met discontinuation criteria but did not discontinue durvalumab (eg, patient withdrew consent, patient became pregnant).
- Deviation 3: The patient received a prohibited concomitant medication or procedure as detailed in Section 6.4 of the CSP or any other concomitant medication or procedure which, upon physician review of all medications and procedures prior to database lock (DBL), is considered to have a potential effect on study outcomes.
- Deviation 4: Missed visits, assessments, or treatments that, in the opinion of the principal investigator,
  - were due to the 2020 COVID-19 global pandemic and
  - there was a significant effect on either completeness, accuracy, and/or reliability of the patient's data, or the patient's rights, safety or well-being.

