### **3.2.3 Adverse Events**

Details of all AEs and SAEs will be collected for a patient from the signing of the informed consent form (ICF) up to 90 days after the last dose of durvalumab. If an event starts after this period and the Investigator considers that it is possible that it is due to a late onset toxicity to durvalumab, then it should be reported as an AE or SAE.

All AEs will be coded using the latest version of Medical Dictionary for Regulatory Activities (MedDRA) providing the System Organ Class (SOC) and Preferred Term (PT).

In addition, all AEs will also be graded according to the National Cancer Institute (NCI) Common Terminology Criteria for AEs (CTCAE Version 4.03) allocating grades from Grade 1 to Grade 4 which will be used for the reporting. The meaning of these categories are as follows:

- Grade 1: Mild AE
- Grade 2: Moderate AE
- Grade 3: Severe AE
- Grade 4: Life-threatening or disabling AE
- Grade 5: Death related to AE

Treatment-emergent adverse events (TEAEs) are AEs that start after the first dose of durvalumab or which start prior to the first dose of durvalumab but worsen following the first dose of durvalumab, and where the start date/date of worsening is also no later than 90 days after the last dose of durvalumab or the initiation of the first subsequent therapy following discontinuation of durvalumab (whichever occurs first). Any TEAE will be included in the AE summaries as detailed in Section 4.5.1.

Missing start and stop dates for AEs will be imputed using the rules described in Section 4.1.3.

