### 3.2.8 Exposure to Durvalumab

The total (or intended) exposure (weeks) of durvalumab is defined as:

- Total treatment duration (weeks) = Total treatment duration (days) / 7

where:

Total treatment duration (days) = [earliest of (last dose date where dose > 0mg + 27 days, death date, cut-off date [DCO]) - first dose date] + 1

The actual exposure (weeks) of durvalumab is defined as:

- Actual treatment duration (weeks) = [total treatment duration (days) – total duration of dose delays (days)] / 7.

Dose reductions are not permitted per the CSP for durvalumab and the actual exposure calculation makes no adjustment for any dose reductions that may have occurred.

As patients are scheduled to receive 1500 mg via IV infusion every 4 weeks (28 days), the duration of dose delays is the sum of all individual dose delays as follows:

- Total duration of dose delays (days) = sum of MAX[0, (date of dose [x+1] – date of dose [x] - 28 days)].

If no delays were encountered, the total duration of dose delays would sum up to 0.

Relative dose intensity (RDI) is the percentage of the actual dose intensity delivered relative to the intended dose intensity through to treatment discontinuation.

RDI is defined as follows:

RDI = 100% \* d/D, where d and D are, respectively, the actual and intended cumulative doses delivered up to the date of durvalumab discontinuation or progressive disease or the data cut-off date, whichever occurs earlier. D is the total dose that would be delivered if there were no modification to dose or schedule.

Percentage intended dose (PID) is the percentage of the actual dose delivered relative to the intended dose through to disease progression.

PID = 100% \* d1/D1, where d1 is the actual cumulative dose delivered up to the earlier of progression (or a censoring event) or the data cut-off date and D1 is the intended cumulative dose up to the earlier of progression (or a censoring event) or the data cut-off date. D1 is the total dose that would be delivered, if there were no modifications to dose or schedule.

When deriving actual dose administered the volume before and after infusion will also be considered.

To illustrate the calculation of RDI, [Table 5](#) shows an example of durvalumab dosing for 4 patients.

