#### **4.2.4 Previous and Concomitant Medications and Procedures**

Prior and concomitant medications and procedures will be listed for all patients in the SAF.

Concomitant medications will be summarized by chemical subgroup (ATC 4th level), and preferred WHO name for the SAF. Patients with the same concomitant medication/procedure multiple times will be counted once per medication/procedure. A medication/procedure that can be classified into more than one chemical and/or therapeutic subgroups will be presented in each subgroup.

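### SAP 3.5.2 closes concomitant therapy on the date of the last infusion, so therapy first started after it is missing from the SAP 4.2.4 concomitant medication summary

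*SAP*

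**What the plan says.** SAP 3.5.2 sets two classes of therapy. Prior therapies are "those with at least one dose/treatment taken before the date of the first dose of study medication". Concomitant therapies are "those with at least one dose/treatment taken between the date of first dose (inclusive) and the date of last dose (inclusive) of durvalumab". There is no third class for therapy begun after treatment ends.

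SAP 4.2.4 uses these classes. It states that "Prior and concomitant medications and procedures will be listed for all patients in the SAF", and it summarises only the concomitant class, by ATC 4th level and preferred name.

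Other windows in the plan close later:

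- Protocol 6.4 has medication reported from screening "until 90 days after last dose of IP". Protocol Table 2 has a concomitant medications row at day 30, month 2 and month 3 after the last dose.
- SAP 3.2.3 counts an adverse event as treatment-emergent if it starts or worsens "no later than 90 days after the last dose of durvalumab or the initiation of the first subsequent therapy following discontinuation of durvalumab", whichever comes first.
- SAP 3.2.8 ends total exposure at the earliest of "last dose date where dose > 0mg + 27 days", death and data cut-off.

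**The concern.** Durvalumab is given as one infusion every 28 days. When a new toxicity or an intercurrent illness ends treatment, it will usually have appeared after the infusion that turns out to be the last. The drugs newly started for it then begin after the concomitant window has closed. An event on day 10 after the final infusion counts as treatment-emergent and falls within exposure, yet the drug given for it is not concomitant.

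The protocol uses the word concomitant for exactly these records in Table 2, so a reader of the study report would expect the table of that name to contain them. This is a safety study, motivated in part by pneumonitis after chest radiotherapy (protocol 4.2.1). Use of antibiotics and of steroids outside the immune-mediated category helps a reader interpret respiratory events. A summary that stops at the last infusion is least complete for patients who stopped early.

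**Working it through.** The plan gives no figure to reproduce here. The check is date arithmetic on the definitions, followed by tracing where a therapy started late would be reported.

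**Inputs.** Dosing interval 28 days (protocol 1.2). Concomitant window: first to last dose, both dates included (SAP 3.5.2). Medication collection: to last dose + 90 days (protocol 6.4). Adverse event window: to last dose + 90 days, or first subsequent therapy if earlier (SAP 3.2.3). Maximum 26 doses (protocol 6.1.2).

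**Length of the windows.** For k doses given on schedule:

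- concomitant window = 28(k − 1) + 1 days
- full adverse event window = 28(k − 1) + 1 + 90 days
- share not covered = 90 / [28(k − 1) + 91]

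| Doses k | Concomitant window (days) | Adverse event window (days) | Share not covered |
|---|---|---|---|
| 1 | 1 | 91 | 90/91 = 98.9% |
| 2 | 29 | 119 | 90/119 = 75.6% |
| 3 | 57 | 147 | 90/147 = 61.2% |
| 26 | 701 | 791 | 90/791 = 11.4% |

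The 90 days is a ceiling, because the adverse event window closes earlier if subsequent therapy starts. A therapy already in use on the last infusion date still counts as concomitant.

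**Effect of a longer window.** Ending it at last dose + 27 days, as for exposure, would leave 90 − 27 = 63 days uncovered. Ending it at last dose + 90 days leaves none.

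**Where a therapy first taken 10 days after the last infusion is reported.**

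- *For an imAE:* absent from the 4.2.4 table. SAP 4.5.1.1 tabulates post-baseline medication associated with imAEs by ATC class, and summarises the length of intervention with steroids, immunosuppressants or hormone replacement. Neither is cut at the last dose.
- *For an AESI that is not an imAE:* absent from the 4.2.4 table. SAP 4.5.1.1 counts patients whose AESI needed steroids, immunosuppressants or endocrine therapy, but does not summarise the individual drugs.
- *For any other event, such as an infection:* absent from the 4.2.4 table, and no other medication summary applies.
- *In all three cases:* SAP 4.1.1 has all collected data listed for treated patients.

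**How many patients.** Protocol 2.3.2.1 reports that about 10% of patients in monotherapy studies stopped for an adverse event. If that carried over, 10% of 100 to 150 treated patients is 10 to 15. The same section reports that pneumonia led 1.1% of PACIFIC durvalumab patients to stop; on 100 to 150 patients that is 1.1 to 1.65, or one or two. These are illustrations. Patients who stop for other reasons can also start new therapy in the 90 days.

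**The case against.** The strongest reply is that little is lost from the report. Four parts of it deserve an answer.

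- **Listings.** Read alone, SAP 4.2.4 lists only prior and concomitant therapy, so a reader might infer that later therapies vanish from the listings too. The documents do not support that. The general rule in SAP 4.1.1 covers all collected data, and SAP 4.5.1 adds intervention, dose and duration to the AESI and imAE listings.
- **Rescue treatment.** A reader might infer that steroid and immunosuppressant use is understated where toxicity was worst. For AESIs and imAEs this does not follow, because the SAP 4.5.1.1 tables are not tied to the last dose date. Pneumonitis is a named AESI (protocol 8.3.12), so a pneumonitis judged not immune-mediated still has its steroid treatment counted. Whether radiation pneumonitis is on the AESI term list cannot be told from these documents.
- **Prohibited medication.** A reader might infer that prohibitions running past the last dose, such as live vaccines to 30 days, would escape Deviation 3. SAP 2.2.1 words that deviation as "The patient received a prohibited concomitant medication or procedure as detailed in Section 6.4 of the CSP", which brings in the protocol's own time limits, and it adds a physician review of all medications before database lock. It does not depend on the 3.5.2 window.
- **Collection and reporting differ.** The protocol sets what is collected, while SAP 3.5.2 sets a reporting category. The exposure and adverse event windows define other quantities. That is fair: this is a mismatch of windows, not a contradiction.

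All four replies stand. They leave untouched the gap in the 4.2.4 table for events that are not imAEs.

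**Conclusion.** The point holds for one descriptive table. As written, the SAP 4.2.4 summary leaves out every therapy first started after the last infusion, although the protocol collects those records under the heading of concomitant medication. For imAEs the loss is made good elsewhere at drug level. For other AESIs it is made good only as counts of patients treated, and for all remaining events it is not made good in any summary.

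The uncovered share of the adverse event window is at most 98.9% after 1 dose, 61.2% after 3 and 11.4% after 26. These shares assume on-schedule dosing and no subsequent therapy within 90 days. They measure time not covered, not the number of medications omitted, which the documents do not allow one to estimate. The infection example also assumes that the event is not on the AESI term list, which is held outside these documents.

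A reader might go further and infer that the safety results themselves are biased. They are not affected by this definition: the primary endpoint and the adverse event counts use their own windows, and causality is the investigator's assessment. This is a consistency point that is worth correcting.

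**What to change.** In SAP 3.5.2, define concomitant therapy as any therapy taken from the first dose to the earlier of last dose + 90 days and data cut-off. Flag therapies started after the last dose, and those started after subsequent anti-cancer therapy, so that the table can also be read on the adverse event window. Use this definition for the 4.2.4 summary. Deviation 3 needs no change.

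The cost is one definition, one end date and two flags in the programming. The data are already collected under protocol 6.4.

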### 3.5.3

CCI

CCI

## 4. ANALYSIS METHODS

### 4.1 General Principles

#### 4.1.1 General Statistical Considerations

The following general statistical considerations will be applied for the analyses and presentation of the data. In case of any specific deviations, methods will be specifically noted on the relevant output.

- All data, demography, baseline characteristics, safety, efficacy and biomarkers, will be summarized using descriptive statistics, as appropriate for the type of data, for the SAF. In addition, all efficacy and safety data and some selected relevant data (eg, patient disposition, demography and baseline characteristics) will be summarised separately for the WHO/ECOG PS 0 to 1 and 2 groups.
- Continuous variables will be summarized by the number of observations (n), mean,

standard deviation, median, minimum, and maximum.

- For the continuous data, the summary statistics will be displayed with the following accuracy (number of dps):
  - The minimum and maximum with same accuracy as the raw data.
  - The mean and median will be rounded to 1 additional dp more than the number of dps in the raw data.
  - The standard deviation will be rounded to 2 additional dps more than the number of dps in the raw data.
  - If the number of observation is 1, the SD will not be derived.
- Categorical variables will be summarized by frequency counts and percentages for each category and percentages will be rounded to one dp.
- As a default, percentages will be calculated using the number of patients who have non-missing data as the denominator. Therefore, percentages for missing data will not be presented in the results. If the denominator is different from this default, it will be explained in a footnote to the output.
- SAS® version 9.3 or higher will be used for all analyses.
- Exact CIs for proportions will be calculated using the Clopper-Pearson method.
- For percentiles of survival times based on the Kaplan-Meier method (eg, median survival), CIs will be calculated using the default method available in the SAS LIFETEST procedure (ie, the Klein and Moeschberger extension of the Brookmeyer-Crowley method).
- For point-estimates of survival based on the Kaplan-Meier method (eg, for PFS12), CIs will be calculated using the default method available in the SAS LIFETEST procedure (ie, using Greenwood's estimate of standard error and a log-log transformation).
- The data will be included in summaries/analyses using the following criteria:
  - All laboratory data, vital signs data that are recorded at unscheduled visits will be included in the summaries using the visit windows defined in Section [4.1.4.1](#).
  - The tumour measurements and PRO data should not be affected by any delays in treatment cycles/dates of start of treatment cycles as it is intended that they are only recorded at pre-scheduled time points. These data will be included in the summaries and analyses of the data using the visit windows defined in Section [4.1.4.2](#).
- All data collected including scheduled, delayed and unscheduled data will be listed in the patient data listings which are produced for all treated patients. They will be ordered by treatment/not treated, centre, WHO/ECOG PS group, patient and visit and, if relevant, timepoint when they were recorded. Patients who are included in the SAF will be flagged. Depending on the availability of the data, all data for the patients who are not treated will be listed separately. They will be ordered by centre, WHO/ECOG PS group, patient and visit and timepoint, if relevant.

- All adverse events will be coded using MedDRA and NCI CTCAE Grade and will be reported using SOC and PT, NCI CTCAE Grade, as appropriate.
- All concomitant and previous medications will be coded using WHO drug dictionary and will be reported using anatomical therapeutic chemical (ATC) classification and generic term.
- Baseline is defined as the last assessment of the variable under consideration prior to the first dose of durvalumab regardless of whether the assessment is on Day 1, Screening or unscheduled.
- Participants affected by the COVID-19 pandemic will be listed as recorded as protocol deviations, which were assessed as COVID-19 related. The study disruptions due to the pandemic will also be summarized. Subject disposition will be summarized including number (%) of patients who discontinued treatment due to the pandemic and who withdrew from study due to pandemic. Important protocol deviations will be summarized including number (%) of patients with at least one important protocol deviation related to the pandemic. Number and percentage of patients with confirmed/suspected COVID-19 infection along with demographic characteristics, medical history and adverse event of patients with confirmed/suspected COVID-19 infection will be presented. If the study has fewer than 5 and/or less than 2% of the patient population with confirmed/suspected COVID-19 infection, then a listing will be presented instead of summary.

#### **4.1.2 General Considerations for Summary of Safety Data**

The following considerations are for the summary of safety data.

- The missing values in vital signs, laboratory data, coagulation and urinalysis will not be imputed.
- If a laboratory value is reported as <LLQ (where 'LLQ' is the lower limit of quantification), then LLQ value will be used to impute '<LLQ' for the summary tables. In the data listings, this value will be listed as reported <LLQ.
- Any TEAEs with missing causality data will be considered as related to the durvalumab.
- Any partial dates will be presented as reported in the data listings. The partial dates will be imputed for the derivation of time to resolution, time to onset etc. using the criteria given in Section 4.1.3.

#### **4.1.3 Handling of Missing Data**

Missing safety data will generally not be imputed. However, safety assessment values of the form of "<x" (ie, below the lower limit of quantification) or >x (ie, above the upper limit of quantification) will be imputed as "x" in the calculation of summary statistics but displayed as "<x" or ">x" in the listings.

If the start date of the concomitant medication or AE is missing, the following rules will be

applied:

- If the year is missing, the year should be imputed as the year that patient received the first dose of durvalumab.
- If the year is available and the month and day are missing, then impute the month as January and the day as 01.
- If the year and month are available and the day is missing, impute the day as 01 (the first day of the month).
- If any of the above puts the date before the date of first dose of durvalumab, a conservative approach is followed and, the date is imputed using the date of first dose.

If the stop date of the concomitant medication or AE is missing, the following rules will be applied:

- If the year is missing, the year should be imputed as the year that patient received the last dose of durvalumab.
- If the year is available and the month and day are missing, then impute the month as December and the day as 31.
- If the year and month are available and the day is missing, impute the day as the last day of the month (eg, 28, 29, 30 or 31).
- If any of the above puts the date after the date of the last dose of durvalumab, a conservative approach is followed and, the date is imputed using the data cut-off date (DCO).
- It is not expected to have missing dates for unscheduled laboratory, diagnostics data. However, if there are missing dates, for any derivations, the dates should be imputed following the rules for concomitant medications and AEs

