### **3.2.3.3 Immune-Mediated Adverse Event**

An imAE is defined as an AESI that is associated with drug exposure and is consistent with an immune-mediated mechanism of action and where there is no clear alternate etiology. In general, imAEs will include AESIs that are managed using steroids, immunosuppressants and/or hormone replacement therapy.

This document comprises the specification for the analysis of the imAEs as identified by the investigator (as recorded in CRF Adverse Events (AE)).

Time to event analyses for imAEs will be performed for the following definitions:

- Time to first onset of imAE: Start date of first imAE episode – First dose date + 1
- Time to first onset of imAE of Grade 3 or 4: First date of imAE episode that had CTCAE Grade 3 or 4 – First dose date + 1
- Time to resolution of imAE: End date of imAE episode – Start date of imAE episode + 1
- Time to resolution of Grade 3 or 4: End date of imAE episode that had CTCAE Grade 3 or 4 – First date imAE episode had severity of grade 3 or higher + 1

If an imAE does not resolve, then the time to resolution will be censored at earliest date of DCO, death date, or last dose date + 90 days. Patients who die prior to resolution of the imAE will be censored at the date of death.

Adjudication and statistical analysis for the imAEs will be performed by AstraZeneca. The results will be incorporated into and discussed in the CSR.

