- At least one imAE leading to treatment interruption
- At least one imAE leading to treatment discontinuation
- At least one imAE by maximum CTCAE Grade
- At least one imAE causally related to study medication
- At least one imAE with fatal outcome

Post-baseline medications associated with imAEs will be presented by number and percent of patients by ATC-classification and PT.

Length of intervention with steroids, immunosuppressants and/or hormone replacement therapy for imAEs will be calculated based on treatment start and stop dates. Total treatment times will then be combined for each patient and summarised for patients experiencing at least one treatment-emergent imAE.

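### For partly missing AE and medication dates, the SAP 4.1.3 overrides ignore the known month and year, which can inflate imAE resolution and steroid durations and move pre-treatment onsets to Day 1

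*SAP*

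**What the plan says.** SAP 4.1.3 gives one set of imputation rules for AEs and concomitant medications.

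- **Stop dates.** The rules are triggered thus: "If the stop date of the concomitant medication or AE is missing". A missing day is handled by: "If the year and month are available and the day is missing, impute the day as the last day of the month". A missing month and day become 31 December. A missing year becomes the year of last dose. The override follows: "If any of the above puts the date after the date of the last dose of durvalumab, a conservative approach is followed". The replacement is the DCO.
- **Start dates.** Missing parts go to the first of the month or to 1 January, and a missing year becomes the first-dose year. Then: "If any of the above puts the date before the date of first dose of durvalumab, a conservative approach is followed". The replacement is the first-dose date.

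These dates are used in analysis. SAP 4.1.2 states: "The partial dates will be imputed for the derivation of time to resolution, time to onset etc". SAP 3.2.3.3 defines "Time to resolution of imAE: End date of imAE episode – Start date of imAE episode + 1". SAP 4.5.1.1 adds: "Length of intervention with steroids, immunosuppressants and/or hormone replacement therapy for imAEs will be calculated based on treatment start and stop dates", with the times then combined per patient. SAP 3.2.3 and 3.5.2 both refer missing dates to 4.1.3.

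A separate rule in SAP 3.2.3.3 covers imAEs that do not resolve. They are censored at the earliest of DCO, death, and last dose plus 90 days.

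**The concern.** Neither override looks at the part of the date that was recorded. For a stop date, the end of the known month is already the latest day the record allows, so replacing it with the DCO is not conservative. It assigns a date that the record rules out.

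The events most exposed are those that matter in this study. AEs are collected for 90 days after the last dose, and an imAE that ends treatment will often resolve in that window. Its stop date, if partial, then falls after the last dose and meets the override. Steroid and immunosuppressant courses given for such events follow the same path, and SAP 4.5.1.1 sets no cap on their length.

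For a start date, a record that can only be pre-treatment is moved to Day 1. Protocol 9.5.2.1 keeps pre-treatment AEs out of the summary tables, and SAP 4.5.1 requires them to be flagged as pre-treatment in listings. The override can work against both.

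**Working it through.** The documents give no figure for this rule, so there is none to reproduce. I applied the text literally to illustrative dates. Duration is end − start + 1, as in SAP 3.2.3.3.

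**1. One resolved imAE.** Assumed: last dose 10 Feb 2020, onset 20 Feb 2020, stop recorded as April 2020.

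- Month-end, 30 Apr 2020: 10 + 31 + 30 = 71 days.
- 30 April is after the last dose, so the DCO replaces it. With an assumed DCO of 15 Jul 2021, 511 + 1 = 512 days. With 15 May 2023, 1,180 + 1 = 1,181 days.
- The same event, never resolved, is censored at last dose + 90 days, 10 May 2020: 80 + 1 = 81 days.

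**2. DCO set by the SAP's own timing.** SAP section 5 places the final analysis after the last patient has had 24 months' opportunity plus 90 days, so every patient's DCO is at about Day 730 + 90 = 820 or later. Assumed: first dose 15 Jan 2020, onset 5 days before last dose, true stop on the 15th of the following month, only that month recorded. The SAP duration is 820 − onset day + 1, and the cap for an unresolved event is 5 + 90 + 1 = 96 days.

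| Last dose | True | Month-end | SAP rule | Unresolved cap |
|---|---|---|---|---|
| Day 29 | 38 | 54 | 797 | 96 |
| Day 85 | 43 | 59 | 741 | 96 |
| Day 169 | 51 | 67 | 657 | 96 |
| Day 337 | 36 | 52 | 489 | 96 |

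A resolved event then counts as lasting 489/96 ≈ 5 to 797/96 ≈ 8 times as long as an unresolved one. At the earliest primary DCO (Day 183) the first two rows become 183 − 24 + 1 = 160 and 183 − 80 + 1 = 104 days, still above 96.

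**3. Events that ended before the last dose.** Onset 1 Apr 2020, true stop 5 Apr, recorded as April 2020, last dose 20 Apr. Month-end (30 Apr) is after the last dose, so the rule gives 743 days at the Day 820 DCO of step 2, against a true 5. A stop known only to the last-dose month meets the override unless the last dose fell on the last day of that month. Over 1 Jul 2019 to 30 Jun 2022 that is 1,060 of 1,096 possible last-dose dates (97%).

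**4. Where the gap is short.** With dosing every 4 weeks and no delay, a patient still on treatment at the DCO has a last dose within about 28 days of it. For a stop known to the month, the error is then days to weeks.

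**5. Start dates.** Assumed: first dose 10 Jun 2020. A start recorded as May 2020 is imputed as 1 May and then moved to 10 June, although it cannot be on treatment. With a complete stop of 25 May 2020, the duration is −16 + 1 = −15 days. A start recorded only as 2020 also becomes 10 June, which is defensible because the record allows it.

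**The case against.** The strongest reply is that little is affected. Protocol 8.3.4 requires start and stop dates for every AE, and Protocol 9.7 provides for queries on missing data. Stop dates touch neither the primary endpoint nor any incidence count, and no hypothesis is tested. The imAE resolution analysis is Kaplan-Meier on one worst episode per patient and category, so a few late values move a median little. All of this stands. It limits the likely effect but does not make the rule correct. Means and maxima of steroid duration remain exposed, and where grades tie and all episodes resolved, SAP 4.5.1.1 selects the longest, which favours an inflated one.

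It could also be said that an event whose stop is set to the DCO would be handled as unresolved and so capped. The SAP does not say so. If it were, a documented resolution would be discarded.

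Several stronger readings are tempting and are not supported:

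- *Every stop date after the last dose is overwritten.* The rules apply only to missing or partly missing dates.
- *Each affected date is wrong by months to years.* Not when the last dose is close to the DCO (step 4). For a late-enrolled patient who completes treatment, the gap to the final DCO is only about three to four months.
- *Pre-treatment AEs definitely become treatment-emergent.* SAP 3.2.3 requires onset after the first dose, and the override sets onset to the first-dose date. The outcome depends on a same-day convention that the SAP does not state.
- *Losing prior-medication status distorts the tables.* SAP 4.2.4 summarises only concomitant medications, and SAP 4.1.2 has listings show partial dates as reported.

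**Conclusion.** The rule is wrong as written for partly missing dates, because it can produce values that the record itself excludes. A partial stop date can add weeks to years to imAE time to resolution and to steroid or immunosuppressant duration, and can take a resolved imAE past the cap set for unresolved ones. Nothing prevents an imputed stop from falling after death. A partial start known to precede first dose is moved to Day 1. It could then be counted as treatment-emergent if same-day onset counts, and a negative duration is possible.

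The 512- and 1,181-day figures rest on assumed DCOs, since the documents give no DCO date. The step 2 figures rest on the earliest DCO that the SAP's timing allows and on assumed dosing and onset dates. All of them describe early discontinuation with a late DCO, which is the unfavourable end of the range. The documents do not say how many dates are partial, so the effect on any table is unknown.

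**What to change.** Amend SAP 4.1.3 as follows.

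- **Partial stop date:** use the last day of the known month, or 31 December of the known year, capped at the earlier of death and DCO. Delete the override to the DCO.
- **Wholly missing stop date:** treat the event as ongoing, and for imAEs apply the censoring rule in SAP 3.2.3.3.
- **Partial start date:** move it to the first-dose date only when the recorded part is compatible (same month and year; same year with month missing; or year missing) and the stop date is not before first dose. Otherwise keep the pre-dose date.
- **Same-day onset:** state in SAP 3.2.3 whether onset on the first-dose date is treatment-emergent.

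The cost is a few lines of SAP text and one derivation macro. No new data are needed.
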